7.1.5.11 Recording of Adverse Events

Adverse events will be recorded and reported from Day 1 to Day 56. Adverse events will be captured at clinic visits on Day 1 and Day 56, and at telephone safety visits on Day 14, Day 28 and Day 42.

When an AE/SAE occurs, it is the responsibility of the investigator to review all documentation (eg, hospital progress notes, laboratory, and diagnostic reports) relative to the event. The investigator will then record all relevant information regarding an AE/SAE in to the eCRF. All details of any treatments initiated due to the AE should also be recorded in the subjects' notes and the eCRF.

Each AE will be documented in the subject's eCRF. If an AE changes in frequency or intensity during a study, a new entry of the event must be made in the eCRF.

In the event where the principal investigator is not a clinician, then the principal investigator must delegate the safety review duty to a clinician.

The investigator will attempt to establish a diagnosis of the event based on signs, symptoms, and/or other clinical information. In the absence of a diagnosis, the individual signs/symptoms should be documented.

All AEs occurring during the study must be documented on the relevant eCRF pages. The following data should be documented for each AE:

- Description of the symptom event;
- Classification of ‘serious’ or ‘not serious’;
- Severity;
- Date of first occurrence and date of resolution (if applicable);
- Action taken;
- Causal relationship;
- Outcome of event (unknown, recovered, not yet recovered, recovered with sequelae, death [with date and cause reported]).

After the initial AE or SAE report, the investigator is required to proactively follow each subject and provide further information to the sponsor on the subjects’ condition.

All AEs are required to be assessed by a medical practitioner. All AEs or SAEs documented at a previous visit/contact that are designated as ongoing, will be reviewed at subsequent visits/contacts. All AEs or SAEs will be followed until resolution, until the condition stabilizes, until the event is otherwise explained, or until the subject is lost to follow-up. The investigator will ensure that follow-up includes any supplemental investigations as may be indicated to elucidate the nature and/or causality of the AE or SAE.

7.1.5.12 Reporting of Device Deficiencies

All device deficiencies related to the identity, quality, durability, reliability, safety or performance of an investigational medical device shall be documented throughout the study. Device deficiencies will be further classified as those that potentially could lead to SADE (device deficiency with SADE potential), and those that could not (device deficiency without SADE potential).

To determine SADE potential, the investigator may consider whether the device deficiency might have led to an important medical occurrence in any of the following situations:

- a) if either suitable action had not been taken;
- b) if intervention had not been made, or;
- c) if circumstances had been less fortunate.

7.1.5.13 Reporting of Serious Adverse Events

As the sponsor has a legal responsibility to notify the appropriate regulatory authorities about the safety of a new therapeutic intervention, prompt notification by the investigator, or nominee, of any SAEs, SADEs or device deficiencies with SADE potential, to the sponsor is required.

All SAEs, SADEs or device deficiencies with SADE potential, whether related or unrelated, and regardless of expectedness, should be recorded on the SAE Form and submitted to the study sponsor within 24 hours of site awareness via email as follows:

- Email to: [contact]

If the investigator learns of any SAE/SADEs/device deficiency with SADE potential, including death, at any other time after a subject completes the study, and he/she considers the event reasonably related to the therapeutic intervention, the investigator will promptly notify the sponsor.

In addition to reporting the SAE/SADEs/device deficiency with SADE potential to sponsor, the investigator must also notify the HREC which approved the study according to their requirements.

Copies of all correspondence relating to reporting of any SAEs/SADEs/device deficiency with SADE potential should be maintained in the site's study files and will be checked routinely by the Study Monitor.

If the sponsor and the investigator consider that the SAE/SADEs/device deficiency with SADE potential is related to the therapeutic intervention (ie, an adverse reaction) and unexpected it will be reported to the appropriate regulatory authorities by the sponsor (or designee) within the pre-defined timelines.

In the event where the principal investigator is not a clinician, then the principal investigator must delegate the safety review duty to a clinician.

Non-serious or expected adverse reactions, or events (without causal relationship to the therapeutic intervention), should be recorded in the eCRF by the investigator as part of International Council for Harmonisation of Technical Requirements for Pharmaceuticals for Human Use (ICH) Good Clinical Practice (GCP), and will be reported to the appropriate regulatory authorities by the sponsor (or designee) as required.

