7.1.5.4 Definition of a Suspected Unexpected Serious Adverse Reaction

A suspected unexpected serious adverse reaction (SUSAR) is a related SAE that is both serious and unexpected as assessed using the current Investigator's Brochure or Product Information.

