7.1.5.10 Relationship of Adverse Events to Investigational Device

The investigator is obligated to assess the relationship between the investigational device and the occurrence of each AE/SAE. The investigator will use clinical judgment to determine the relationship. Alternative causes, such as natural history of the underlying diseases, concomitant therapy, other risk factors, and the temporal relationship of the event to the device use will be considered and investigated.

The causal relationship of the AE to the investigational device or study procedures should be assessed by the investigator (or medically qualified delegate) using the following classifications:

- Not Related: In the investigator's opinion, there is not a causal relationship between the investigational device and the AE.
- Unlikely: The temporal association between the AE and investigational device is such that the investigational device is not likely to have any reasonable association with the AE.
- Possible: The AE follows a reasonable temporal sequence from the time of use of the investigational device but could have been caused by the study subject's clinical state or other modes of therapy administered to the subject.
- Probable: The AE follows a reasonable temporal sequence from the time of use of the investigational device, and cannot be reasonably explained by the known characteristics of the study subject's clinical state.

Adverse events that have a relationship (possible or probable) to the investigational device, are termed ADEs.

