9.5 Safety Analysis

9.5.1 Adverse Event Analysis

Adverse events will be coded using the Medical Dictionary for Regulatory Activities (MedDRA). AEs will be grouped by system organ class and preferred term and summarized, by treatment group at the time of onset of the AE (ie, the therapeutic intervention most recently prior to the onset of the AE). The summary tables will present the number and percentage of total subjects and number of events, by system organ class and by preferred term.

All AE summaries will be restricted to treatment emergent AEs only. Treatment emergent AEs are defined as AEs which commence on or after the time of start of therapeutic intervention.

For the summaries of AEs, subjects who experience the same AE (in terms of the MedDRA preferred term) more than once will only be counted once for that event in the number of subjects but all occurrences of the same event will be counted in the number of events.

Separate summaries will be provided for AEs by severity and relationship to study intervention.

Serious adverse events will be summarized and listed separately.

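### The timed regulatory-report rule in 7.1.5.13 needs sponsor and investigator to agree, and tests device events only against the exercise or stretching intervention, which conflicts with the protocol's own SUSAR and device-effect definitions

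*Protocol*

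**What the plan says.** Protocol 7.1.5.13 sets up several reporting steps.

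- **Site to sponsor.** This step takes in every serious event and SADE, and any deficiency that could lead to a SADE. Its wording is "whether related or unrelated, and regardless of expectedness, should be recorded on the SAE Form and submitted to the study sponsor within 24 hours". The clock starts when the site learns of the event.
- **Site to ethics committee.** The investigator also notifies the HREC, according to its requirements.
- **Sponsor to regulator, timed.** The condition is "If the sponsor and the investigator consider that the SAE/SADEs/device deficiency with SADE potential is related to the therapeutic intervention" (glossed there as an adverse reaction), "and unexpected it will be reported to the appropriate regulatory authorities by the sponsor (or designee) within the pre-defined timelines".
- **Sponsor to regulator, residual.** "Non-serious or expected adverse reactions, or events (without causal relationship to the therapeutic intervention), should be recorded in the eCRF by the investigator", and these "will be reported to the appropriate regulatory authorities by the sponsor (or designee) as required".
- **After the subject has completed the study.** The investigator promptly notifies the sponsor of an event that he or she considers reasonably related to the therapeutic intervention.

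The definitions sit elsewhere. Section 7.1.5.4 states: "A suspected unexpected serious adverse reaction (SUSAR) is a related SAE that is both serious and unexpected", with expectedness read from the Investigator's Brochure or Product Information. Table 3 classifies events the same way. Section 7.1.5.9 gives causality for the intervention to the investigator or a medically qualified delegate. For devices, 7.1.5.10 adds a separate assessment: "The investigator is obligated to assess the relationship between the investigational device and the occurrence of each AE/SAE". Section 7.1.5.6 defines an unanticipated SADE. Section 6.1 describes the therapeutic intervention as graded exercise delivered through ClearPlay, with passive stretching as the other listed intervention. Section 2.2 presents ClearHeart and ClearNeck as two further devices, used for testing.

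**The concern.** The timed-report sentence does not match the definitions that feed it, in two respects.

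First, it turns a judgement that the protocol gives to the investigator into a joint one, and no rule says what happens when the two parties differ. The sponsor is also unblinded (6.3.1), as is everyone else in this open-label trial.

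Second, it names device effects and device deficiencies as its subject but applies a causality test that belongs to the exercise and stretching programmes. The separate device-causality judgement required by 7.1.5.10, and the unanticipated-SADE category in 7.1.5.6, feed into no timed step.

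At stake is whether staff who follow 7.1.5.13 as written would send a disputed SUSAR, or an unanticipated serious effect of a prototype test device, to the regulator on the timed route. This is operative text of the protocol. A statistical analysis plan would not repair it.

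**Working it through.** No arithmetic applies: the point rests on no rate, effect size or sample size. The check is to take each kind of serious, unexpected event and follow it through the two regulatory routes in 7.1.5.13.

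**What each route requires**

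- Timed route: sponsor *and* investigator consider the event related to the therapeutic intervention, and it is unexpected.
- As-required route: the event is (a) a non-serious reaction, or (b) an expected reaction, or (c) an event without causal relationship to the therapeutic intervention. I take (c) as standing on its own, which is the reading kinder to the protocol.

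**Cases (all serious and unexpected)**

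1. *Both parties say related to exercise or stretching.* The timed route applies. The rule works.
2. *Investigator says related to exercise or stretching, sponsor says not.* By 7.1.5.4, Table 3 and 7.1.5.9 this is a SUSAR, since the investigator's judgement makes it related. The timed route fails because the joint condition is not met. In the as-required route, (a) and (b) fail by construction, and (c) is met only if the sponsor's view overrides the investigator's, which no section says. The event is clearly in neither route.
3. *Investigator says not related, sponsor says related.* The timed route again fails. Limb (c) is met only on the investigator's view. The protocol is silent on which view governs.
4. *Both agree that the event was caused by ClearHeart or ClearNeck alone.* By 7.1.5.2 and 7.1.5.10 it is a device effect, and by 7.1.5.6 an unanticipated one. It is not related to exercise or stretching, so the timed route fails even though the sentence names SADEs. It meets (c) and goes to the as-required route, which it shares with non-serious events and which has no stated timeline.
5. *A serious device effect of ClearPlay, the app that delivers the intervention.* This can be judged related to the therapeutic intervention, so the timed route can apply.
6. *A ClearHeart- or ClearNeck-only serious effect learned of after the subject has completed the study.* The post-study sentence rests on the investigator's judgement alone, so the joint condition is not at issue. It still asks only about the therapeutic intervention, so it does not call for this event to be notified even to the sponsor.

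Cases 2 and 3 show the first conflict. Cases 4 and 6 show the second. Case 5 marks its limit: the gap concerns the two test devices, not every device event.

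**The case against.** The strongest reply is that the safeguards around this sentence are substantial. During the study every serious event and SADE reaches the sponsor within 24 hours whatever its cause. The investigator notifies the HREC without needing the sponsor's agreement. Section 7.1.5.13 opens with the sponsor's legal responsibility to notify authorities, and 12.2 requires compliance with Therapeutic Goods Administration regulations and GCP as well as with the protocol. The timed route itself gives no number of days. Since the sentence names SADEs and device deficiencies, its causality phrase looks incomplete rather than meant to exclude devices. All of this stands, and it rules out several stronger inferences:

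- *That regulatory reporting occurs only on joint agreement.* There is a second route; the joint condition governs the timed one.
- *That the sponsor can veto a SUSAR.* The classification in 7.1.5.4 does not depend on the sponsor. What disagreement can block, on a literal reading, is the timed report.
- *That device events can never qualify.* Case 5 shows that they can.
- *That events can be withheld from regulators in full compliance with the protocol.* Section 12.2 brings in the governing regulations.
- *That device-relatedness will not be tabulated*, because 9.5.1 says "Separate summaries will be provided for AEs by severity and relationship to study intervention". That sentence does not exclude a device table, and 9.2 leaves analysis detail to the SAP, which is not at hand.

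The reply does not remove the mismatch. The as-required route does not clearly take in a disputed event, a general duty to comply does not say whose judgement starts the timed report, and notifying the HREC is not a report to the regulator.

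**Conclusion.** The concern holds as an internal contradiction in one operative sentence, with a narrower echo in the post-study sentence. As written, a serious, unexpected event on which sponsor and investigator disagree has no clear regulatory route. An unanticipated SADE caused only by ClearHeart or ClearNeck is sent to the route without a stated timeline.

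The size is qualitative. The protocol gives no serious-event rate, so the number of affected reports cannot be estimated. A reader might multiply subjects, visits and devices, but that counts exposures, not misrouted events. The device risks listed in 2.4 are hand or arm discomfort in particular groups. No efficacy estimate is affected.

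The conclusion rests on three readings: the word *and* in the trigger is taken literally; *therapeutic intervention* has the meaning given in 6.1; and ClearHeart and ClearNeck count as investigational devices. Sections 7.1.5.2 and 7.1.5.10 list no devices by name, but 2.2 calls both of these devices, and 7.5.1 and 7.6.1 call them commercial prototypes.

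**What to change.** Amend two sentences in 7.1.5.13.

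- In the timed-report sentence, replace the joint condition with *If either the sponsor or the investigator considers*, and extend the causality phrase to *related to the therapeutic intervention or an investigational device*.
- In the post-study sentence, add *or an investigational device* after the reference to the therapeutic intervention.

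The first change settles disagreement and brings the rule into line with 7.1.5.4, Table 3 and 7.1.5.9. The second makes use of the device judgement that 7.1.5.10 already requires, so no new data are collected. The cost is a short wording amendment and possibly a few more expedited reports.

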7.2 Biomarkers

Samples will be collected at Baseline and Week 8. The following biomarkers will be assessed:

- Structural proteins [t-tau, NF-L, GFAP and UCH-L1]
- Inflammatory cytokines [IL-6, IL-10 and TNF α]
- Single nucleotide polymorphisms [APO-E4, BDNF, and NFkB]

Analyses will be performed by Monogram Biosciences/ LabCorp for structural proteins (t-tau, NF-L, GFAP, and UCH-L1) and inflammatory cytokines (IL-6, IL-10, and TNF-alpha).

Samples may be collected as follows:

- Blood collection by direct venipuncture is the preferred option;
- Buccal swab and collection of saliva if subject is needle phobic.

A detailed description of sample handling and processing of samples will be provided in the Study Procedures Manual.

7.3 BioBank

Genetics will be evaluated at a future date as a supplemental component of this study.

A blood or saliva sample for DNA and RNA isolation will be collected at baseline and a blood or saliva sample for RNA isolation will be collected at Week 8 from subjects who have consented to participate in the BioBank project. Participation is optional. Subjects who do not wish to participate in the genetic research may still participate in the study. Separate consent will be obtained for this sample collection.

Genetic variation may impact a subject's response to study intervention, susceptibility to, and severity and recovery from mTBI. Research will be limited to genetic, epigenetic and transcriptomic factors that will inform prognosis and aid in evaluation of clinical outcomes in mTBI. Therefore, where local regulations and IRB/IEC allow, a blood OR saliva sample will be collected for DNA and RNA analysis from consenting subjects. A blood sample is the preferred option, if agreeable to the subject.

Genetic research may consist of the analysis of 1 or more candidate genes or the analysis of genetic markers throughout the genome [or analysis of the entire genome] (as appropriate).

DNA samples will be analyzed for single nucleotide polymorphisms and RNA for RNAseq analyses. Additional analyses may be conducted if it is hypothesized that this may help further understand the clinical data.

The samples will be analyzed as part of a multi-study assessment of genetic factors involved in the clinical outcomes of mTBI.

The results of genetic analyses will not be reported in the clinical study report or provided to subjects.

The sponsor will store the DNA samples in a secure storage space with adequate measures to protect confidentiality.

The samples will be retained while research on mTBI continues but no longer than 5 years or other period as per local requirements.

Details on processes for collection and shipment and destruction of these samples can be found in the Study Manual.

7.4 Neuropsychology Testing

7.4.1 Post-Concussion Symptom Scale

The PCSS is a well validated 21-item self-report measure that records symptom severity using a 7-point Likert scale of severity. It ranks possible concussion symptoms by their severity to determine if a concussion has occurred, and whether further evaluation is required.

For all subjects, daily reported PCSS scores collected from ClearPlay© mobile application will be utilized to determine the resolution of symptoms.

This scale will be used to identify post-concussion symptom burden of each subject daily.

7.4.2 Godin Leisure Time Exercise Questionnaire

The Godin leisure-time exercise questionnaire is a well validated activity scale. It asks subjects to rate their exercise as either mild, moderate or strenuous, and will provide an indication for how each subject perceived the exercise allocated to them.

This scale will be used to identify the degree of self-reported athletic exertion of each subject weekly.

7.4.3 Beck Anxiety Inventory

The Beck Anxiety Inventory (BAI) enables clinicians to measure the severity of anxiety in adolescents and adults. The BAI has been found to discriminate well between anxious and non-anxious diagnostic groups in a variety of clinical populations.

Subjects respond to 21 items rated on a scale from 0 to 3, each item is descriptive of subjective, somatic, or panic-related symptoms of anxiety.

This scale will be used as a predictor of anxiety-induced prolongation of PPCS.

7.4.4 Brief Symptom Inventory-18

The Brief Symptom Inventory (BSI)-18 is an instrument that evaluates psychological distress and psychiatric disorders in people. The test can be used for areas such as subject progress, treatment measurements, and psychological assessment.

The BSI-18 is a 53-item self-report scale that uses the 5 point Likert scale.

This scale will be used as a predictor of anxiety-induced prolongation of PPCS.

7.4.5 Reiss-Epstein-Gursky Anxiety Sensitivity Index

The Reiss-Epstein-Gursky Anxiety Sensitivity Index (ASI) is a 16-item scale that focuses on apprehension about the symptoms of anxiety itself.

The ASI is a good predictor of anticipatory and situational anxiety-induced prolongation of PPCS.

7.4.6 Conners' Adult Attention Deficit Hyperactivity Disorder Rating Scale

The Conners' adult attention deficit hyperactivity disorder (ADHD) Rating Scale (CAARS) provides a multimodal assessment of symptoms and behaviors associated with ADHD in patients.

The CAARS is a well validated diagnostic instrument to identify ADHD, which is a predictor of PPCS.

7.4.7 Center for Epidemiologic Studies - Depression Scale

The Center for Epidemiologic Studies - Depression Scale (CES-D) is a brief self-report scale designed to measure self-reported symptoms associated with depression. The items of the

scale are symptoms associated with depression which have been used in previously validated longer scales.

The CES-D is a well validated diagnostic instrument to identify depression, which is a predictor of PPCS.

7.5 Autonomic Tests

7.5.1 Cold Pressor Test (Ice Bucket and ClearHeart© Testing)

The cold pressor test measures the cardiovascular response to acute cooling of the hand. The cold pressor test will be performed using 2 different tests, with a break in-between each test (refer to Section 8.1 for details of the order of assessments to achieve this).

Ice Bucket Testing: The subject will rest in the supine position for at least 3 minutes. The subject will be fitted with the Caretaker4® device which attaches to right arm and right finger and measures continuous beat to beat HR and BP. Once connected, 5 minutes of baseline data collection will occur, followed by 2 minutes data collection while the subjects' left hand will be submerged in ice water for 120 seconds (ice bucket testing), and a further 2 minutes post-ice bucket data collection.

Testing with ClearHeart©: ClearHeart© is ANSwers Neuroscience Pty Ltd commercial prototype for cold pressure testing. The subject will rest in the supine position for at least 3 minutes. The subject will be fitted with the Caretaker4® device which attaches to right arm and right finger and measures continuous beat to beat HR and BP. Once connected, 5 minutes of baseline data collection will occur, followed by 2 minutes data collection while the subjects' left hand will be placed in the hand cooling device (ClearHeart©) for 120 seconds, and a further 2 minutes ClearHeart© data collection.

